7.1.6 Echocardiogram/ Multigated Acquisition Assessments

For patients with prior history of anthracycline treatment that are enrolled on the PF-04518600 (OX40) Arms B or C, an echocardiogram (ECHO) or multigated acquisition (MUGA) scan will be performed at screening, every 3 cycles (starting at Cycle 4 Day 1), and End of Treatment (if not performed within 3 months of discontinuation).

7.1.7 Cardiac Enzyme Monitoring

For patients with prior history of anthracycline treatment that are enrolled on the PF-04518600 (OX40) Arms B or C, cardiac enzyme monitoring will be performed at screening, Day 1 of every cycle, and End of Treatment.

Troponin T and N-terminal of the prohormone brain natriuretic peptide (NT-proBNP) will be evaluated in patients with previous history of anthracycline treatment. Assessments must be performed prior to dosing. No need to repeat on Cycle 1 Day 1 (C1D1) if the screening assessment is performed within 2 days prior to that date. Assessments performed on Cycle 2 Day 1 and Day 1 of each subsequent cycle should be performed within 48 hours prior to dosing. Assessments should also be performed when clinically indicated.

7.2 Tumor Response Assessments

Objective response will be evaluated based on RECIST criteria Version 1.1 and irRECIST using CT scan or MRI scan or PET-CT scan. For patients with multiple measurable lesions, up to 5 lesions in total and 2 lesions per organ should be identified.

For Arm D (radiation), radiated target lesions will be evaluated with a modified version of the international criteria proposed by the RECIST Committee, version 1.1.

The exact technique used for measurement of lesions (i.e., either CT or MRI or PET-CT scan) will be left to the discretion of the investigator, however, for each patient the same technique must be used throughout the study, assessed whenever possible by

the same individual. The CT/ MRI abdomen must include the pelvis. A PET/CT is allowed, but ultrasound and x-ray of thorax is not allowed.

In cases where there is suspicion of progression before the next scheduled assessment, an unscheduled tumor assessment should be performed. In case a detected increase in tumor size is below the resolution limit of the CT/ MRI scanner, it is accepted to continue with treatment until a second assessment at a later time point unequivocally confirms progressive disease. Partial response requires confirmation with a follow-up scan at least 4 weeks apart.

If the increase in tumor burden is $\geq 20\%$ relative to nadir, then in the absence of rapid clinical deterioration, confirmation by a repeat, consecutive assessment no less than 4 weeks from the date first documented is recommended. Patients will continue with study drug until confirmation scan is obtained.

The following are defined as non-target lesions: bone lesions, leptomeningeal disease, pleural/pericardial effusion, ascites, inflammatory breast disease, lymphangitis, cystic lesions and lesions not measurable by CT or MRI. All non-target lesions are described over time and need not be measured.

The first evaluation of disease status by imaging will be done after 2 cycles or 8 weeks (± 7 days) of treatment and every 2 cycles or 8 weeks (± 7 days) thereafter at the physician's discretion. After completion of 1 year of treatment, tumor assessments will be performed every 3 cycles or 12 weeks (± 7 days) during treatment, independent of cycle delays.

Patients will also be eligible for the study if their disease is evaluable outside irradiated field on CT/ MRI.

In case palliative radiation becomes necessary during the treatment within the study, there must be at least two target lesions left outside the irradiated field for continuous assessment for response.

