	</= 28 Days prior to 1 st Dose of Radiation	First Day of Radiation (+/- 3 Days)	Day 1 (+/- 2 Days)	Day 15 (+/- 2 Days)	Day 1 (+/- 2 Days)	Day 15 (+/- 2 Days)	Day 1 (+/- 2 Days)	Day 15 (+/- 2 Days)	30 Days after Last Dose of Study Drug (+/- 7 Days)	Every 12 Weeks (+/- 7 Days)
Informed Consent ¹	X									
Verify Eligibility Criteria	X	X								
Medical History ²	X									
Tumor History	X									
Serum or Urine Beta- hCG ³	X	X			X		X		X	
Protocol /Safety Evaluation										
Physical Exam and ECOG ⁵	X	X	X	X	X	X	X	X	X	
Height ⁶	X									
Weight ⁶	X		X	X	X	X	X	X		
Vital Signs ⁶	X	X	X	X	X	X	X	X	X	X
12-lead ECG ⁷	X		X		X		X			

Assessments		Treatment Period							Post-Treatment	
	Screening	Radiation Lead-in ⁴	Cycle 1		Cycle 2		Cycle 3 and Beyond		End of Treatment (EOT)	Follow-Up Visits
	</= 28 Days prior to 1 st Dose of Radiation	First Day of Radiation (+/- 3 Days)	Day 1 (+/- 2 Days)	Day 15 (+/- 2 Days)	Day 1 (+/- 2 Days)	Day 15 (+/- 2 Days)	Day 1 (+/- 2 Days)	Day 15 (+/- 2 Days)	30 Days after Last Dose of Study Drug (+/- 7 Days)	Every 12 Weeks (+/- 7 Days)
AE/SAE Assessment ⁸	X	X	X	X	X	X	X	X	X	X
Concomitant Medications	X	X	X	X	X	X	X	X	X	X
Survival Status ⁹										X ⁹
Laboratory Evaluation										
Hematology ¹⁰	X	X	X	X	X	X	X	X	X	X
Chemistry ¹¹	X	X	X	X	X	X	X	X	X	X
Thyroid Function ¹²	X							X ¹²		X
Urinalysis ¹³	X	X			X		X			
Coagulation Test ¹⁴	X	X			X		X			
Hepatitis B and C Testing (Hepatitis B surface antigen and core antibody; anti-hepatitis C antibody)	X									
Study Treatment										
Arm D: XRT ¹⁵		X								
Arm D: Avelumab Dosing ¹⁶				X	X	X	X	X		
Arm D: Utomilumab (4-1BB) ¹⁷			X		X		X			
Tumor Measurement										
CT or MRI or PET-CT ¹⁸	X							Every 8 Weeks for up to 1 year, then Every 12 Weeks thereafter		Every 12 Weeks

Assessments		Treatment Period							Post-Treatment	
	Screening	Radiation Lead-in ⁴	Cycle 1		Cycle 2		Cycle 3 and Beyond		End of Treatment (EOT)	Follow-Up Visits
	</= 28 Days prior to 1 st Dose of Radiation	First Day of Radiation (+/- 3 Days)	Day 1 (+/- 2 Days)	Day 15 (+/- 2 Days)	Day 1 (+/- 2 Days)	Day 15 (+/- 2 Days)	Day 1 (+/- 2 Days)	Day 15 (+/- 2 Days)	30 Days after Last Dose of Study Drug (+/- 7 Days)	Every 12 Weeks (+/- 7 Days)
Tumor Markers (if applicable) ¹⁹	X						Every 8 Weeks for up to 1 year, then Every 12 Weeks thereafter			Every 12 Weeks
Correlative Studies										
Arm D: Tumor Biopsy ²⁰	X ²²						X		X	
Arm D: Immune Biomarkers ²¹	X		X	X	X		X		X	

Footnotes

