2.2.2 Secondary and Exploratory Endpoints

- Objective response rate determined by radiographic disease assessments per RECIST v1.1 and irRECIST.
- Progression-free survival, defined as the time from Cycle 1 start date until the earliest date of disease progression, as determined by investigator assessment of objective radiographic disease assessments per RECIST v1.1 and irRECIST, or death due to any cause, if occurring sooner than progression.
- Duration of response determined by radiographic disease assessment, defined as the time from earliest date of disease response until the earliest date of disease progression per RECIST v1.1 and irRECIST, or death due to any cause, if occurring sooner than progression.
- Overall survival determined from the Cycle 1 start date until death due to any cause.
- Response data in irradiated and non-irradiated lesions.
- Evaluation of various immune biomarkers from tumor and blood biospecimens.

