3.2.4 Arm D: Avelumab + Utomilumab (4-1BB) + Radiation

In the dose escalation phase, the dose of radiation will be de-escalated in combination with fixed doses of utomilumab (4-1BB) and avelumab to evaluate the safety, tolerability, and MTD in patients with advanced solid tumors.

Once the MTD or RP2D is determined, the Arm D MTD expansion will enroll up to 14 patients at the previously established safe dose for additional safety and correlative studies to establish the RP2D for this combination.

Radiation will be administered to 1-3 metastatic sites. This will be de-escalated from a total of 24 Gy to 21 Gy. The technique will be stereotactic radiation via intensity-modulated radiation therapy (IMRT) or Volumetric modulated arc therapy (VMAT). The radiation lead-in will occur within Days -5 to -1 with a +/- 3 day window. There will be 3 fractions or days of radiation. In all cases, the radiation must initiate and end within the radiation lead-time. Cycle 1 Day 1 study drug treatment should begin within 3 days of last dose of radiation.

Utomilumab (4-1BB) will be administered at the fixed flat dose of 100 mg IV on Day 1 of each 28-day cycle or every 4 weeks. Avelumab will be administered at the fixed dose of 10 mg/kg IV on Day 15 of Cycle 1 and Days 1 and 15 of each subsequent 28-day cycle or every 2 weeks. Premedications will be administered per institutional standard.

On days when both avelumab and utomilumab are administered, avelumab will be administered first.

Patients will be restaged at the end of every two cycles and tumor response evaluation will be based on RECIST 1.1 and irRECIST. Patients may be allowed to continue treatment after two cycles of avelumab combinations if there is continued clinical response or disease stabilization and patients do not have significant toxicities. Following radiation, a patient may continue treatment on this combination therapy until the patient experiences confirmed disease progression, unacceptable adverse event(s), intercurrent illness that prevents further administration of treatment, and/or treatment is discontinued following investigator's decision to withdraw the patient, pregnancy, patient withdraws consent, noncompliance with trial treatment or procedure requirements, or administrative reasons.

Table 6: Dosing for Arm D: Avelumab + Utomilumab (4-1BB) + Radiation

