10. Negative serum pregnancy test in women of childbearing potential within 7 days of first dose of treatment and patients of child-bearing potential must agree to use effective contraception during and after 90 days post dose. A woman of childbearing potential is defined as a premenopausal female capable of becoming pregnant. This includes women on oral, injectable or mechanical contraception; women who are single and women whose male sexual partners have been vasectomized or whose male sexual partners have received or are utilizing mechanical contraceptive devices.

11. Subjects must have biopsiable disease. For Arms A, B, and C, subjects must have at least two lesions amenable to biopsy and response evaluation. For Arm D subjects should have at least three lesions amenable to biopsy, response evaluation, and radiation. Tumor lesions used for biopsy should not be lesions used as RECIST target lesions. However, if patients in Arm D do not have three separate lesions, patients will be eligible if there are two lesions, in which one is > 2 centimeters (short axis) and can be used for both biopsy and response evaluation.
12. Subjects must give informed consent according to the rules and regulations of the individual participating sites.

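### Section 7.2 speaks of irradiated target lesions in Arm D under undefined modified criteria, in conflict with Section 7.3, so local radiation shrinkage can count as response

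*Combined protocol and SAP*

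**What the plan says.** Target selection is set in Section 7.2 for all arms: for patients with several measurable lesions, "up to 5 lesions in total and 2 lesions per organ should be identified". Irradiated lesions are not excluded. For Arm D the section adds that "radiated target lesions will be evaluated with a modified version of the international criteria proposed by the RECIST Committee, version 1.1". Neither that section nor any other says what the modification is.

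On radiation, Section 3.2.4 states: "Radiation will be administered to 1-3 metastatic sites". It is given in a lead-in before Cycle 1 Day 1. The Arm D Schedule of Assessments puts the baseline scan at screening, in a window of up to 28 "Days prior to 1 st Dose of Radiation".

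On endpoints, Section 2.2.2 lists "Objective response rate determined by radiographic disease assessments per RECIST v1.1 and irRECIST", and defines PFS and DOR from the same assessments. Clinical benefit in Section 2.1.1 is CR, PR, or SD lasting more than six months. Sections 9.2, 9.3, 9.5.1 and 9.7 use these outcomes without restricting which lesions count. Section 2.2.2 also lists "Response data in irradiated and non-irradiated lesions", but the corresponding comparison is an exploratory objective in Section 2.1.3.

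Other text points the opposite way. Section 4.1, criterion 11, says: "For Arm D subjects should have at least three lesions amenable to biopsy, response evaluation, and radiation". Section 7.3 repeats this, asks that biopsied lesions be kept apart from the RECIST targets, and adds that the irradiated lesion is itself biopsied whenever tissue is taken. For palliative radiation during the study, Section 7.2 requires that "there must be at least two target lesions left outside the irradiated field for continuous assessment for response".

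**The concern.** A RECIST response is read from the change in the sum of target diameters since baseline. If a lesion in that sum is irradiated after the baseline scan, its local shrinkage lowers the sum whether or not the drugs act elsewhere. Arm D's ORR, DOR and clinical benefit could then mix a local radiation effect with the systemic effect, and shrinkage in the field could offset growth outside it when progression is judged from the sum.

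Two uses of the data make this matter. Section 3.5 bases the recommended phase 2 dose partly on preliminary efficacy. In Section 9.7, clinical benefit is the outcome class in the primary CD8 ROC analysis, which combines cohorts with and without radiation. A patient classed as benefiting because of in-field shrinkage would carry a different meaning there from a patient in Arms A to C.

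**Working it through.** The plan states no figure for this point, so the main check is textual.

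1. **Can an irradiated lesion be a target?** Section 7.2 speaks of irradiated target lesions, and its selection rule has no exclusion. Section 7.3 implies the opposite: biopsied lesions should not be targets, and the irradiated lesion is biopsied. The two conflict.
2. **Does Section 7.3 settle it?** Not fully. The wording is advisory. It speaks of one irradiated lesion, while Section 3.2.4 allows one to three sites. The two-lesion exception in Sections 4.1 and 7.3 lets one lesion serve for both biopsy and response, which waives the biopsy/target separation.
3. **Does radiation fall inside the change from baseline?** Yes. The Arm D screening scan precedes the first fraction.
4. **Does any endpoint or analysis section remove these lesions?** No: Sections 2.1.1, 2.2.2, 9.2, 9.3, 9.5.1 and 9.7 are silent.

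The sizes below are illustrations. They assume a 30% fall in the sum for PR, which the documents do not give. The shrinkage values are also assumed.

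- **Shrinkage that alone gives PR.** With stable non-irradiated targets and irradiated share *f* of the baseline sum, the shrinkage needed is 0.30 / *f*: 0.30 / (1/3) = 90%; 0.30 / (1/2) = 60%; 0.30 / (2/3) = 45%; and 30% if every target is irradiated.
- **Masked growth.** Irradiated lesion 40 to 20 mm, non-irradiated lesion 40 to 48 mm. The second alone grows 8/40 = 20%, the increase named in Section 7.2. The sum goes from 80 to 68 mm, or −12/80 = −15%, so it shows no progression.
- **ORR.** Section 9.2 gives up to 14 patients per expansion cohort, so each such patient adds 1/14 = 7.1 points. Exact 95% intervals: 0/14, 0 to 23.2%; 2/14 = 14.3%, 1.8 to 42.8%; 4/14 = 28.6%, 8.4 to 58.1%.
- **CD8 ROC analysis.** Section 9.7 states 90% power for an AUC of 0.69 against 0.5 with 98 patients, half benefiting. With the Hanley-McNeil variance, 49 per class and two-sided 5% alpha, the standard errors are 0.0586 (null) and 0.0534 (alternative). Power is Φ[(0.19 − 1.96 × 0.0586) / 0.0534] = 92.0%, close to the stated 90%. Now suppose *m* of the 49 patients without benefit are classed as benefiting through local shrinkage unrelated to CD8. The observed AUC is (49 × 0.69 + *m* × 0.50) / (49 + *m*):

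| *m* | AUC | Power |
|---|---|---|
| 0 | 0.690 | 92.0% |
| 2 | 0.683 | 89.7% |
| 4 | 0.676 | 86.9% |
| 7 | 0.666 | 82.2% |

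The 98 is the plan's own figure (7 cohorts of 14), used as it stands.

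**The case against.** The strongest reply is that the plan may already deal with this. Section 7.2 gives irradiated lesions their own modified criteria, and the modification could be the very handling that seems to be missing. A reader might infer from the phrase about irradiated target lesions that they do enter the patient-level response. The text does not say so, and this part of the objection stands: bias is possible, not shown. But an undefined rule cannot be checked, and two assessors could score the same scans differently.

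Second, the lesion roles in Sections 4.1 and 7.3 suggest that the irradiated lesion was never meant to be a target, and Section 7.2 also accepts patients whose disease is evaluable outside the field. This is good evidence of intent. It is not a rule for scoring response, and it contradicts the Arm D sentence in Section 7.2.

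A reader might also take the palliative-radiation rule to mean that irradiated lesions leave the sum. It does not say that. It requires two targets to remain outside the field, and it does not cover study radiation.

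Third, radiation is part of the Arm D regimen, the secondary objective concerns the treatment combinations, and there is no between-arm test. A whole-regimen ORR is a legitimate target if labelled as such. That is fair for ORR, but the plan does not label it so. The argument is weaker for the CD8 analysis, where clinical benefit is pooled across arms with and without radiation.

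**Conclusion.** The point holds as a conflict and an undefined rule with a possible bias behind it. Section 7.2 contemplates irradiated target lesions under unstated criteria, Section 7.3 and criterion 11 imply that they should not be targets, and no endpoint or analysis section resolves it. Local shrinkage can therefore count towards Arm D's ORR, DOR and clinical benefit, and can reach the primary CD8 analysis.

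The documents do not support the stronger reading that Arm D's response rate is necessarily inflated. Nor do they show that PFS is lengthened: masking acts only through the target sum, while new lesions, non-target progression and death still count, and in-field regrowth or swelling could act the other way.

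The size cannot be derived. The figures of 60% shrinkage for a PR and 7.1 points per patient rest on an assumed 30% threshold; the 60% also assumes two equal targets with the other stable, and the 7.1 points a cohort of 14. The loss of ROC power depends on an assumed number of misclassified patients. The change is worth making before the Arm D analysis.

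**What to change.** Reconcile Section 7.2 with Section 7.3 and Section 4.1 criterion 11, and write out the modified criteria. Then state in Sections 7.2 and 9.5.1 that:

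- Arm D target lesions are chosen from non-irradiated lesions, with at least one at baseline, and ORR, DOR, PFS and clinical benefit use that sum;
- irradiated lesions are still measured at each scan and reported under the exploratory irradiated versus non-irradiated comparison;
- unequivocal progression inside the field still counts as progression for the endpoints, so that leaving these lesions out of the sum does not lengthen PFS;
- an all-lesion ORR is shown as a sensitivity analysis, which also serves readers interested in the whole regimen.

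The same scans are used and treatment is unchanged, but this is more than SAP wording. Section 7.2 is the protocol's assessment section and targets are picked at baseline. It also says that non-target lesions need not be measured, so irradiated lesions need an explicit measurement rule. Some patients entered under the two-lesion exception will have a single target lesion, and Arm D's ORR may be lower.

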7.3 Biopsy Analyses

For patients in the MTD expansion cohorts of Arms A-C, tumor tissue will be obtained pre- treatment (baseline), between Cycle 1 Day 12-15 (prior to study drug dosing), prior to Cycle 3 Day 1 study drug dosing, and at progression (if achieved stable disease \geq 6 months, partial response, or complete remission) provided there is technically biopsiable tumor, and it is safe for patient to undergo biopsy.

For patients in the escalation cohorts of Arm C (patients enrolled prior to Version 05), tumor tissue will be obtained pre- treatment (baseline), prior to Cycle 2 Day 1 dosing, and at progression (if achieved stable disease \geq 6 months, partial response, or complete remission) provided there is technically biopsiable tumor, and it is safe for patient to undergo biopsy.

For patients in the de-escalation and MTD Expansion cohort of Arm D, tumor tissue will be obtained pre- treatment (baseline), prior to Cycle 3 Day 1 dosing, and at progression (if achieved stable disease \geq 6 months, partial response, or complete remission) provided there is technically biopsiable tumor, and it is safe for patient to undergo biopsy.

Correlative studies for biomarker analyses will be performed during this study.

A fresh core needle biopsy (CNB) will be obtained solely with the purpose of research studies (pre-treatment samples) and sent to the Institutional Tissue Bank (ITB) immediately after collection. Up to 5 cores will be obtained from the CNB procedure. The number of cores obtained will be affected by the patient clinical condition at the time of biopsy and determined by the radiologist who is performing the procedure. It is important to note that in some of these trials, the biopsy sample will also be required for clinical diagnosis. In such case, the first specimen will be prioritized for clinical specimen processing. In most instances, a rapid on site evaluation (ROSE) is available locally to evaluate the adequacy of clinical sample, thus additional biopsies may be procured for this research project. Nevertheless, the amount tissue available for correlative studies can be variable. Core biopsy is typically performed using 21-18 gauge needle and with condition permitting, up to 5 cores should be collected.

For Arms A, B, and C, subjects must have at least two lesions amenable to biopsy and response evaluation. Tumor lesions used for biopsy should not be lesions used as RECIST target lesions. Every effort will be made to biopsy the same lesion at each time point.

For Arm D, subjects should have at least three lesions amenable to biopsy, response evaluation, and radiation. Tumor lesions used for biopsy should not be lesions used as RECIST target lesions. Every effort will be made to biopsy the same lesion at each time point. In addition, the radiated lesion will also be biopsied at each time point. However, if patients in Arm D do not have three separate lesions, patients will be eligible if there are two lesions, in which one is > 2 centimeters (short axis) and can be used for both biopsy and response evaluation.

7.4 Biomarker Analyses

Biomarker analyses will be performed to investigate biomarkers that are potentially predictive of response with the combination of avelumab and an immune modulator. In addition, biomarker studies of tumor and blood biospecimens will be carried out to help further understand the mechanism of action of the avelumab plus the study treatments, as well as potential mechanisms of resistance.

For the MTD Expansion cohorts of Arms A-C, blood samples will be collected at baseline, between Cycle 1 Day 12-15 (prior to study drug dosing), prior to Cycle 3 Day 1 study drug dosing, and at the time of progression (if patient had an initial response of stable disease ≥ 6 months, partial response, or complete remission) to evaluate biological response or predictive markers in blood, tumor, and tumor environment and their relationships to drug exposure, clinical response, or other biologic response markers. Cell free DNA from patient's blood samples will also be analyzed.

For the escalation cohorts of Arm C (patients enrolled prior to Version 05), blood samples will be collected at baseline, prior to Cycle 2 Day 1 dosing, and at the time of progression (if patient had an initial response of stable disease ≥ 6 months, partial response, or complete remission) to evaluate biological response or predictive markers in blood, tumor, and tumor environment and their relationships to drug exposure, clinical response, or other biologic response markers. Cell free DNA from patient's blood samples will also be analyzed.

For the de-escalation and MTD Expansion cohort of Arm D, blood samples will be collected at baseline, prior to Cycle 1 Day 1, prior to Cycle 1 Day 15, prior to Cycle 2 Day 1 dosing, prior to Cycle 3 Day 1 dosing, and at the time of progression (if patient had an initial response of stable disease ≥ 6 months, partial response, or complete remission). Cell free DNA from patient's blood samples will also be analyzed.

The plan for biomarker analyses in Arms A-D is the following:

Immunohistochemistry (IHC): The samples collected will be analyzed by IHC analysis of tumors for markers that may include, but are not limited to, PD-L1, CD3, CD4, Foxp3, CD25, CD8, CD68, CD56, CD20, CD45RO and granzyme B. We may also include PD-L2, B7-H3, B7-x/H4, galectin 9, HVEM and CD48 to measure in tumors and PD-1, 2B4, LAG-3, Tim-3 and BTLA in TILs.

Multiplex IF Analysis: Up to 10 immune markers, 2 panels may be utilized. Currently, there are 2 Vectra panels optimized: Panel#1, CD3, CD8, CD68, PD-L1, PD-1 pan-cytokeratin and DAPI; Panel #2, CD20, CD45RO, FOXP3, Granzyme B, CD57, pan-cytokeratin and DAPI. For multiplex IF analysis, we will use the Opal chemistry and multispectral microscopy Vectra system (Perkin-Elmer) which includes the Nuance software; analysis will be performed using the InForm software. Additional markers will be selected according the results of the gene expression analysis and may include other immunotherapy targets (e.g., OX-40, Vista, GITR, TIM-3, LAG-3, NKp46/CD16, etc.) and proliferation markers (e.g., Ki67).

Molecular Analyses (in Tissue and Blood): Using FFPE tumor tissues and blood samples, Immuno-oncology (IO) gene panels will be examined using the Nanostring technology (nCounter). This assay will be used to measure expression levels of drug targets, tumor infiltrate composition, and total immune cell composition using a single section of FFPE tumor tissue. Next Generation Sequencing (NGS) analysis: To study tumor molecular abnormalities, fresh, and alternatively, FFPE tumor tissues and blood samples before and after treatment will be examined for targeted gene panel NGS (analysis of mutations, copy number, indels, and translocations), whole exome sequencing (WES) and RNA sequencing (Illumina Hi-seq platform).

Flow Cytometry of Blood: Collected blood will be analyzed by flow cytometry for lymphocyte subsets in PBMCs. This flow cytometry panel includes: (1) FACS phenotyping for CD4+ and CD8+ naïve (TN), central memory (TCM), effector-memory (TEM) and terminally differentiated effector (TTDE) cells; (2) Staining for suppressor cells such as CD4+ T-regulatory cell and myeloid derived suppressor cells (MDSC) subsets; (3) Phenotyping of NK cells and (4) Identification of APC subsets (pDC, mDC, B cells, macrophages). To detect and enumerate these populations we have developed FACS cell surface and intracellular staining panels on samples that are analyzed using a FACScanto II flow cytometer (BD Biosciences). These staining panels include antibodies against pan-leukocytes (CD45), T cells (CD4, CD8, CD25, CD27, CD28, CD45RA, CD45RO, CD62L, CD69, OX40, 41BB, CCR7, GB, PFN), CD4+ T-reg cells (CD4, CD25, Foxp3, CD127, CD27, CD62L, CTLA-4, GARP, ICOS, CD39, and LAP), B cells (CD19 CD20), pDC and mDC (CD11c, CD11b, BDCA2, CD123, CD86, CD80, CD83, HLA class II), monocyte/macrophages (CD14, CD11b, CD13), MDSCs (CD33, CD11b, CD14, CD15, HLA-DR, S100A9) and NK cells (CD16, CD56, CD69, NKG2D).

Flow cytometry of freshly disaggregated tumor tissue: Fresh tissue will be available for flow cytometry analysis on larger tumor samples only using Core 3. This will include assessment of the proportion of various immune cells by gating on the pan immune marker CD45 and sub-gating on cell specific markers defining T cell, MDSC, macrophage, DC or NK cell subsets. The expression of checkpoints or their ligands can be explored on each of those cell subsets. In addition, for tissue samples, live

cells can be sub-gated on the CD45-negative fraction to exclude immune cells. EPCAM will be used as a marker of tumor cells and CD90 as a fibroblast marker. The expression of CD80, CD86, GITR-L, ICOS-L, MIC A/B, B7-H3, B7-H4, CD73, PD-L2 and OX40L can all be assessed.

Serum Cytokine Analyses: Cytokines (IFN- γ , IL-1 α , IL-2, IL-4, IL-5, IL-8, IL-10, IL-12p70, IL-13, and TNF- α) will be measured in the serum using the Meso Scale Discovery Platform (Rockville, MD). This technology allows for the detection of up to 40 analytes per well and uses a very low sample volume. This method has a sensitivity up to 1000 fold higher than traditional ELISA assays with a large linear range of 3-4 logs. The instrument performs immunoassays utilizing electrochemiluminescence to detect the signal in a 96 well plate format. This technology can be utilized for either single agent detection or in multiplex format. A wide menu of validated single or multiplex kits for the detection of 1 to 40 analytes are available from the manufacturer and can be customized.

Liquid Biopsy Analyses: For cfDNA, both ultra-deep next-generation sequencing (NGS) mutation analysis of a panel of 50 genes (CMS50) (Ion Torrent PGM and Ion Proton), as well as uniplex or multiplex digital droplet PCR (ddPCR, BioRad and Raindance) are available using 40-50 ng of DNA extracted from 4-5 ml of plasma (blood, purple top).

